To demonstrate the feasibility and impact of shared care on patient experiences and outcome, waiting times and the capacity to better handle the mental health problems at an early stage within primary care. Shared care means a Norwegian adjusted model of the Family Health Team model developed in Hamilton, Canada, where GPs, clinicians and other professionals from primary care and specialized mental health care working together as a team co-located in primary care. The adjusted model of shared care will be tested against current practice in a cluster randomized trial.

Work packages (WPs)

WP1 will investigate current practice and areas for improvement of services and collaboration, based on data extracted from the electronic registers in the collaborating services and on survey data from patients and health care workers.

WP2 will be done by the collaborating services supported by the research group. The Family Health Team model of shared care will be adjusted to the Norwegian context, based on results of WP1 and a study visit to Canada. Then the adjusted model will be implemented, and the implementation process and facilitators and barriers for implementation will be investigated.

WP3 will compare implemented shared care to current practice regarding access to services, distribution of patients, patient experiences and outcome, and distribution of tasks and competences. We will use a difference-in-difference model with randomised clustering of GPs regarding shared care or current practice.

The research group has received financial support from the Regional Health Authority in South-Eastern Norway to initiate this research on shared care, and this money will cover WP2 and parts of WP1. (See attached pdf-file with budget). This application is for a PhD research fellow for WP1 and a postdoc research fellow for WP3, and some support for data collection in WP3.

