During 2013 there have been discussions between the CMHC and the boroughs on how to improve the collaboration between the primary care and the specialized mental health care, and the services are finding that the model of shared care may be adjusted to the local context. Some GPs have also been involved in these discussions, and the GPs in the research group will approach the GP groups in the boroughs during this winter with specific invitation to six GP groups (two in each borough) with altogether approximately 24 GPs to participate in the project.

Cohort definitions and methods common for WP1 and WP 3

In WP1 and WP3 we will collect data from two similar cohorts of patients and in similar ways. This is outlined here and referred to in the descriptions of WP1 and WP3 below.

We will recruit approximately 24 GPs working in two different GP group practices in each of the three boroughs listed above. These GPs must be willing to take part in both WP1 and WP3, and they must be willing to be randomized (as groups) to be involved in shared care or continue with current practice.

Register Cohort

Register Cohort: All patients 16-65 years old and seen by the 24 GPs during 12 months. The reason for choosing 12 months is to have a long enough period to get enough data on referrals between services.

Variables: Age, gender, marital status, borough, GP, referrals, ICPC-2 codes/ICD-10 diagnoses, GAC scores, GP consultations, outpatient consultations and inpatient stays in specialized mental

health and substance abuse services, type of ward/team, use of coercion, codes on treatment procedures, social care, employment, sick leave and prescriptions of medication.

Data collection: Data are extracted from the GP patient records, accident and emergency clinics in Oslo, Akershus University Hospital (specialized mental health and substance abuse services for adults and youth), NAV (the social care, work/sick leave and social security agency). Data

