Estimated size of the Clinical Cohort: Building on the estimated size of the Register Cohort (above), we estimate that the 24 GPs will see altogether 1800 patients during 4 weeks, as 4 weeks are 1/11 of the 44 weeks a year that the GP is required to run their practice. If 75 % give consent to take part in the study on patient satisfaction and outcome, this will be 1350 patients.

Estimated size of the Health Worker Cohort: Approximately 24 GPs, 40 clinicians at outpatient clinics and mobile teams and 60 mental health and social workers in the boroughs is expected to fill in the questionnaire on experiences of current practice, needs for improvements and shared care.

Handling of completed questionnaires and data files

Completed questionnaires from the Clinical Cohort will be kept locked in a safe place at each GP group and collected weekly by the PhD candidate or other members of the research group. The data will be registered by project coordinators in the R&D Department in the Division of Mental Health Services, Akershus University Hospital, in a data base on the approved and secure research server dedicated to research data in Akershus University Hospital. The anonymous data files from the Register Cohort will also be saved on the same dedicated research server at the hospital.

Approval of the project

Application is sent in February 2014 to the Regional Committee on Ethics in Health Research (REK) for approval of the project, including extracting data from the electronic registers and for having the data linked by NAV. The data file that will be made available for the research group will be anonymous.

WP1: Study of current practice and needs for improved collaboration

The aim for WP1 is to study current practice and study needs for improved collaboration. These results will also be used as a baseline in the before-and-after design to control for differences among sites in the comparative study in WP3.

Research questions for WP1

1. What are the characteristics of patients seen in the current practice (ICPC-2 codes, mental health problems, drug problems, functioning, service utilization, quality of life)?
2. What are the patterns of collaborative contacts and activities?
3. How satisfied are patients with the services they receive and the collaboration between them?
4. What do the GPs, primary care and mental health services want and need regarding collaboration and competence?

Design of WP1

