5. Is co-morbidity (somatic, substance abuse) better identified and treated with the Norwegian shared care model than in current practice?
6. Are there competences in service providers that promote closer collaboration?
7. Are GPs and other services more satisfied with the Norwegian shared care model than with their earlier practice?
8. What is the patient course and outcome with the Norwegian shared care model compared to current practice?
9. What is the impact on the patient experience?
10. Also increase in collaboration between GPs and primary health care?

Design of WP3

See above for descriptions common to WP1 and WP3, as well as definitions of the cohorts.

Cohorts in WP3

The Register Cohort in WP3 will be all patients seen by the 24 recruited GPs (see above) from January 1st 2016 to December 31st 2016. The data will be extracted from the registers for the same period of time. This is the year after the implementation during 2015 of the adjusted model of shared care. The data extraction will be done in February 2017. The Clinical Cohort in WP3 will be patients seen by the 24 GPs during four weeks in January 2016. The Health Worker Cohort in WP3 will be the 24 GPs and the clinicians and health workers in the other agencies in January 2016.

Cluster randomized controlled trial

WP3 is a cluster randomised study. Two GP groups in each of the three boroughs will be randomised to take part in the implementation of shared care or continue with their current practice. The randomisation will be done in the summer of 2014, so that some GPs randomised to shared care may take part in the planned study visit to Canada in September 2014 to see the Family Health Team model in operation. The GPs randomised to current practice may take part in implementing shared care after the research study if the model proves to be successful.

Power calculations for the Clinical Cohort in WP3

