Power calculation with 90 % power and CSQ as primary outcome measure shows that to detect a difference of half a SD (3.8) in patient satisfaction between shared care and current practice, we need 85 patients in each arm in a controlled trial with randomisation of individuals. For a cluster randomised trial with ICC=0.03 and 12 GPs in each arm, we need 101 patients in each arm (9 or more per GP). Calculation is done as defined for cluster randomised trials in health services research (Eldridge & Kerry 2012), with elaboration of the CONSORT statement in relation to cluster randomised trials (Schultz et al 2010, Moher et al 2010).

Statistical analyses

Standard statistical analyses will be used to describe various parts of the material, test significant differences, and analyse explanatory models. Growth curve or multilevel analyses will be done of individual progress, with data on the use and services (including collaboration) as explanatory variables. Statisticians at the Research Centre, Akershus University Hospital will give advice and assist with more complex analyses, such as growth curve analysis.

The project plan, project management, organization and cooperation

Principal Investigator is [name], head of the The R&D Department, Division Mental Health Services, Akershus University Hospital (Ahus). The department has 7 senior researchers (3 psychiatrists, 1 child/adolescent psychiatrist, 3 psychologists). One is professor and two are associate professors at the University of Oslo. There are 12 PhD research fellows and a research support staff. Implementation and quality of mental health services is one priority area, and experiences of users and carers another. The department is co-located with the Health Services Research Centre, with statisticians and ICT experts on patient data extraction.

Project group (see also CVs)

[name], Principal Investigator. Head of R&D Department Mental Health Services, Akershus University Hospital (Ahus), specialist in psychiatry and professor at the Clinic for Health

Services Research and Psychiatry, Institute of Clinical Medicine, University of Oslo. He has been medical director and psychiatrist at a pioneering CMHC with close collaboration with primary care, and he has extensive experiences in mental health services research.

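### The 101 patients per arm are sized for a single post-implementation comparison, but the protocol names a difference-in-difference model for WP3; the two statements need to agree

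*Protocol*

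**What the plan says.** Under the heading Power calculations for the Clinical Cohort in WP3, the protocol takes CSQ-8 as primary outcome with 90 % power. It sizes the trial "to detect a difference of half a SD (3.8) in patient satisfaction between shared care and current practice": 85 per arm under individual randomisation and, with ICC 0.03 and 12 GPs per arm, "we need 101 patients in each arm (9 or more per GP").

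Two other places describe a design with a baseline period. Under Work packages (WPs), the scope is "WP3 will compare implemented shared care to current practice regarding access to services, distribution of patients, patient experiences and outcome", and the method is given as "We will use a difference-in-difference model with randomised clustering of GPs regarding shared care or current practice". Under WP1: Study of current practice and needs for improved collaboration, the WP1 results are to be "used as a baseline in the before-and-after design to control for differences among sites in the comparative study in WP3".

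The two Clinical Cohorts come from the same 24 GPs but are recruited separately, in four weeks of May/June 2014 (WP1) and four weeks of January 2016 (WP3). Estimated sizes of cohorts expects 1350 consenting patients, about 675 per arm at equal allocation. The Statistical analyses paragraph does not return to difference-in-difference; it says "Growth curve or multilevel analyses will be done of individual progress".

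**The concern.** A difference-in-difference estimate subtracts the WP1 between-arm difference from the WP3 one. Because the WP1 patients are a separate sample, the estimate carries the sampling error of both differences, offset only as far as GP effects persist from one period to the next. The power paragraph has no WP1 sample size and no between-period correlation, so it sizes a different quantity from the one the work-package summary names.

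Two things are at stake. A reader who follows the work-package summary would take 101 per arm as enough for 90 % power, which over most of the range of r it is not. And the protocol leaves two incompatible descriptions of the WP3 comparison of patient experiences, which includes the primary outcome.

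**Working it through.** **Inputs from the protocol.** Effect 0.5 SD (3.8 points, so SD 7.6); power 90 %; ICC = 0.03; k = 12 GPs per arm; 101 per arm; expected 1350/2 = 675 per arm in a Clinical Cohort.

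**Assumptions.** Two-sided 0.05 (not stated, but it reproduces 85; one-sided 0.05 would give 69). Different patients in the two periods. Between-period correlation of GP effects r from 0 to 1 (not in the protocol). The WP1 size of 675 per arm applied to WP3 as well where stated. Normal approximation unless noted.

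**1. The protocol's own figure.** Individual randomisation: 2 × (1.960 + 1.282)² / 0.5² = 84.06, so 85. Clustered: 85 × [1 + (85/12 − 1) × 0.03] = 100.5, so 101. This is a one-time-point formula. As a check, in SD units, the variance of the post-only difference with N per arm is

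2 × [(1 − ICC)/N + ICC/k].

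At N = 101: 2 × [0.97/101 + 0.03/12] = 2 × 0.01210 = 0.02421, SE 0.1556, power 89.5 %. At 9 per GP (108 per arm) it is 91.0 %. For that contrast the printed claim holds.

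**2. Difference-in-difference.** With n₃ per arm in WP3 and n₁ per arm in WP1, the variance is

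2 × [(1 − ICC)(1/n₃ + 1/n₁) + 2 × ICC × (1 − r)/k].

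Example, n₃ = 101, n₁ = 675, r = 0: 2 × [0.97 × (1/101 + 1/675) + 2 × 0.03/12] = 0.0321, SE 0.179, power 79.7 %.

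| Per arm, WP3 / WP1 | r = 0 | r = 0.5 | r = 0.8 | r = 1 |
|---|---|---|---|---|
| 101 / 675 | 79.7 % | 86.0 % | 89.7 % | 92.0 % |
| 101 / 101 | 62.3 % | 67.0 % | 70.1 % | 72.3 % |
| 675 / 675 | 97.9 % | 99.8 % | >99.9 % | >99.9 % |

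In the first row the estimate is as precise as the post-only one when 2 × r × ICC/k equals the variance of a WP1 arm mean: r = 0.003937/0.005 = 0.79. With t on 22 df that row is 76–90 %, but the post-only power at 101 is then 86.7 % too.

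**3. What difference-in-difference would need.** With equal numbers in both periods, 90 % power requires 282, 207, 179 and 164 per arm per period at r = 0, 0.5, 0.8 and 1. At r = 0 that is 282/675 = 42 % of the expected cohort, so over half could be lost to follow-up before power fell below 90 %.

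**4. Adjustment for the WP1 cluster mean.** The post-only variance is multiplied by 1 − ρ², where ρ is the correlation between a GP's WP1 and WP3 means: ρ² = (r × ICC/k)² / (v₁ × v₃), with v = (1 − ICC)/n + ICC/k in each period. With 101 in WP3 and 675 in WP1, v₃ = 0.01210 and v₁ = 0.003937. At r = 1, ρ² = 0.0025²/(0.003937 × 0.01210) = 0.131 and power is 93.2 %; at r = 0 it is the post-only 89.5 %. With 101 in both periods the range is 89.5–90.7 %.

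**The case against.** The strongest reply is that the contradiction is soft. The work-package summary applies difference-in-difference to WP3 in general, and no sentence says that the primary CSQ-8 test takes that form. The WP1 wording about controlling for site differences fits baseline adjustment equally well, and under adjustment 101 holds. The choice of primary estimator is also something a protocol may leave to its analysis plan.

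Much of this stands, and it limits the point. It does not remove it: the summary lists patient experiences within the scope of WP3 and names one model directly afterwards, and nothing in the protocol reconciles that with the power paragraph. The complaint is about two statements in one document that disagree, not about detail left for later.

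Three stronger readings are tempting and not supported:

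- *That power at the stated minimum is 62–72 %.* This needs WP1 to be held to 101 per arm. The power paragraph concerns the WP3 cohort only, and the protocol expects about 675 per arm in WP1.
- *That 101 is right only for a post-implementation comparison.* With 675 per arm in WP1 and r of about 0.8 or more, difference-in-difference also reaches about 90 %; baseline adjustment keeps 101 roughly right at any r.
- *That the trial is too small.* Nothing makes 101 a recruitment target, and the expected cohort gives ample power on the protocol's own inputs.

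All figures keep the power paragraph's GP as cluster. The protocol randomises GP groups ("they must be willing to be randomized (as groups")). Which unit the calculation should use is a separate question and lends no weight here.

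**Conclusion.** The point holds as a minor inconsistency. The printed requirement is correct for a single post-implementation contrast and does not in general carry over to the difference-in-difference model the protocol names. For that model, 101 per arm in WP3 gives 80–92 % power with WP1 at its expected size, with 90 % reached only at r of about 0.8 or more, a value the protocol neither states nor supports. With 101 per arm in both periods, no value of r restores 90 %.

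The consequence is confined to the stated minimum and its power. At 675 per arm in both periods, power is at least 97.9 % (96.7 % with t on 22 df), before loss to follow-up. These figures rest on two-sided 0.05, ICC 0.03 at GP level, 12 GPs per arm, separate patients in each period and r between 0 and 1.

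**What to change.** Make the work-package summary, the WP1 baseline sentence and the power paragraph describe the same comparison. There are two ways.

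- **Preferred.** Name as primary the WP3 between-arm difference in CSQ-8 adjusted for the WP1 cluster mean, with difference-in-difference as a supporting analysis. The 101 per arm then roughly holds (89.5–93 %, normal approximation). It uses data already planned, and its variance is never larger than that of the post-only comparison. The price is one between-cluster degree of freedom, which matters if few clusters are analysed.
- **Otherwise.** Keep difference-in-difference and restate the requirement for it, giving the patients per arm assumed in both WP1 and WP3 and a range for the between-period correlation.

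Either way the cost is wording in three places and one recalculation. With the GP as cluster, no change to planned recruitment follows.

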2.1. Background and status of knowledge

Definition and potential advantages of shared care

Kates et al (2011a) define collaborative mental health care as “care that is delivered by providers from different specialties, disciplines, or sectors working together to offer complementary services and mutual support. As in any effective partnership, common goals, clear and equitable decision making, and open and regular communication are keys.”

Effective collaboration is essential both within and between primary care, mental health care and substance abuse care. Lack of coordination between health care levels has, however, been pointed out repeatedly by consumer organizations and health authorities. In Norway, primary care and GPs are funded through municipalities/boroughs and specialised mental health care through state owned health authorities. This split and the activity based financing in both primary care (GPs) and specialist care adds to the challenges of collaboration. This also creates selection problems because both hospitals and GPs will have (financial) incentives to attract profitable patients (cream- skimming) and to skimp and/or dump unprofitable patients by referring them to the other health care level.

Current knowledge regarding shared care

Research-based knowledge about the effect of shared care is inconclusive. A Cochrane review by Smith et al. (2009) concluded that there was insufficient evidence to demonstrate significant benefits from shared care apart from improved prescribing. In another Cochrane review (Harkness and Bower 2009) the effects of on-site delivered psychological therapy to patients in primary care resulted in reductions in primary care provider consultations, prescribing costs, and rates of mental health referrals. However, the changes were modest and inconsistent resulting in unclear clinical or economic significance of the results. A review conducted by Butler et al. (2011) concluded that integrated care appeared to improve depression management in primary care patients, but not necessarily symptom improvement.

Research on collaboration has mainly been in the area of depression and anxiety, and then primarily on simpler models of collaboration between two parties, usually a doctor and nurse (Hviding et al.

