2008, Craven et al 2006) or between a therapist and a GP (von Orden et al. 2009). Some of the most important factors in the collaboration between health care seems to be the establishment of collaborative relationships, shared goals, a structured organization of collaboration, and co-location or close physical proximity of collaborators (Seaburn et al. 1996).

The general practitioner (GP) is a key person in primary care (Lampe et al 2012), including for mental health. Most referrals to specialized health services are done by the GP, and the GP is also important in referring to and collaborating with primary mental health care in the municipality. There is great variation in how GPs work with mental illness, partly depending on their interest, but also depending on the support the GP may receive from other professionals and services (Fleury et al 2012a, 2012b). In Norway the field of primary mental health care with teams of mental health workers has been extensively developed during the last 10-15 years, but there seems to be a large variation in the degree of collaboration between GPs and these primary mental health care teams.

According to user organizations, the lack of collaboration is an important area for improvement, as both patients and their families frequently experience fragmentation of health services. There have been various forms of collaboration in Norway between Community Mental Health Centres (CMHCs), GPs and primary health and social care. But with a lack of rigorous research on such models, we have little knowledge on how they function and whether they contribute to better patient satisfaction and better outcome.

Family Health Teams – a model that will be adjusted to the Norwegian context

The Family Health Team shared care model as developed in Hamilton, Canada, offer a promising model of shared care (Kates 2011a, 2011b). This is built around GP practices. Each team include one or more GPs in addition to nurses, mental health counsellors, a visiting consultant psychiatrist, and some other part-time staff (pharmacist, nutritionist, physiotherapist, occupational therapist). Team members are co-located and provide coordinated health care for both physical and mental

illness. This enhances primary care staff's ability to treat more patients, in turn resulting in fewer referrals to secondary and tertiary specialised services.

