The goal is to provide comprehensive health care close to where the patient lives, with minimal fragmentation and with the ability to integrate the treatment of co-morbid somatic and mental diseases. This model has significantly increased access to care for individuals with mental health and addiction problems and reduced waiting times. It has reduced the use of in-patient and out-patient mental health services, improved communication and co-ordination and is greatly appreciated by patients who also find it less stigmatizing. It has also demonstrated significant improvement in up to 70% of patients, and GPs feel more confident and skilled in treating mental health problems (Kates 2011a, 2011b).

The model is consistent with the aims of the Norwegian Collaboration Reform by offering more assessments and treatment within primary care by close collaboration, including with resources from mental health services and the municipality/borough. It is anticipated that the model is well suited to serve patients and families from ethnic minority who in general show higher prevalence of mental illness yet lower use of specialist services (Ayazi & Bøgwald 2008).

2.2.Approaches, hypotheses and choices of methods

The setting for the project

Alna, Grorud and Stovner are three boroughs in the north-eastern part of Oslo. They are served by DPS Groruddalen (Community Mental Health Centre) and other departments in Division of Mental Health Services of Akershus University Hospital (Ahus). As shown in the attached letters, the boroughs and the CMHC are committed to test an adapted model of shared care. The boroughs are among those in Norway with the highest proportion of people from ethnic minorities, providing an opportunity to focus attention on how these populations' needs can be met.

Populations and number of GP group practices in the boroughs are shown in the table below.

Borough	Population	Immigrants*	GP groups	Number of GPs
Alna	47 000	22 000 (47%)	11	37
Grorud	26 000	11 000 (42%)	5	20
Stovner	31 000	14 000 (45%)	4	22
Total	104 000	47 000 (45%)	20	79

**) Including first generation immigrants*

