extraction from GP records and the accident and emergency clinics are done by [name], who is a member of the research group and has a company (Mediata) specializing in such data extraction with extensive experience from other studies. Data from electronic hospital patient records will be extracted by ICT engineers in the Research Support Centre of the hospital, following procedures used in several previous studies. Data from the other registers are ordered from these according to their procedures. All data files will include the personal identity number used in Norway, and they will be linked by NAV. The research group will receive an anonymous data file.

Clinical Cohort

Clinical Cohort: Patients 16-65 years old seen by the 24 GPs during 4 weeks within the 12 months of the Register Cohort, and giving written consent to participate in the outcome study. This includes filling in a one page questionnaire at the index consultation, receiving a similar questionnaire 3 and 9 months later, and giving consent to link the data on the questionnaires to the data from the Register Cohort described above. The questionnaire after 3 months will measure short term outcome and satisfaction, and the questionnaire after 9 months will measure longer term outcome and satisfaction. From experiences in earlier studies with similar procedures in GP practices, we expect that 70-80 % will give consent (probably somewhat lower for immigrants).

Variables: Age, gender, borough, GP, satisfaction with health services (CSQ-8), mental health problems (CORE-10), substance abuse (CAGE-4), waiting time, experience of collaboration. The primary outcome measure in the cluster randomized trial will be the Client Satisfaction Questionnaire (CSQ-8), which has been used extensively in research (Larson 1979). The secondary outcome measures will be CORE-OM 10 (10 items, Barkham 2013), which is a short form of the now well established questionnaire CORE-OM on mental health problems. It has excellent psychometric properties and is available in Norwegian.

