See above for descriptions common to WP1 and WP3, as well as definitions of the cohorts.

Cohorts and periods for data collections in WP1

Register Cohort in WP1 will be all patients seen by the 24 GPs from July 1st 2013 to June 30th 2014. The data will be extracted from the registers for the same period of time. The data extraction will be done in September 2014. Clinical Cohort in WP1 will be patients seen by the 24 GPs during four weeks in May/June 2014. Health Worker Cohort in WP1 will be the 24 GPs and the clinicians and health workers in the other agencies in May 2014.

WP2: Adapting and implementing the Norwegian model for shared care

WP2 will be done by the collaborating services supported by the research group. The Family Health Team model of shared care will be adapted to the Norwegian context, based on results of WP1 and a visit to Canada to learn more about the model. In this process we follow advice given by the Medical

Research Council in UK regarding the needs to adapt models to the local context as a part of research (Craig et al 2008). Then the Norwegian model will be implemented, and the implementation process and facilitators and barriers for implementation will be investigated.

A suggested outline of the framework for a model for shared care

Following discussions in the research group and with some of the services interested in trying a model of shared care, a suggested framework for a model may be: Shared care is implemented by developing a multidisciplinary team of health and social workers from the primary mental health care, the outpatient clinic of the CMHC and social care (NAV). There should be rooms available for the team within or close to the GP groups taking part in shared care.

There may be one team serving all the three GP groups, or there may be separate teams or sub- teams. If there are separate teams, some of the resources may be shared by the teams.

The teams may include persons full time or part time, and it may have access on a regular or ad hoc basis to persons working in other services not represented in the team.

The process of defining and deciding on design of the adjusted shared care model

The Norwegian shared care model will be specified late in the autumn of 2014 based on the following sources of information:

- Analyses of the patterns of distribution and referrals between the GPs, primary mental health care, social care and specialised mental health services.

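### Is the half-SD target for CSQ-8 a fault in the power calculation because it has no stated rationale and no detectable difference is given for the expected cohort?

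*Protocol*

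**What the plan says.** Under the heading "Power calculations for the Clinical Cohort in WP3", the protocol takes CSQ-8 as the primary outcome and 90 % power, and sets out "to detect a difference of half a SD (3.8) in patient satisfaction between shared care and current practice". It needs 85 per arm with individual randomisation. With an ICC of 0.03 and 12 GPs per arm it states "we need 101 patients in each arm (9 or more per GP".

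The population is given under Clinical Cohort: "Clinical Cohort: Patients 16-65 years old seen by the 24 GPs during 4 weeks within the 12 months of the Register Cohort", with written consent and no mental-health criterion. Estimated sizes of cohorts expects 1800 patients seen in the four weeks and, at 75 % consent, 1350 participants. The power section does not use that number.

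The sections Cohort definitions and methods common for WP1 and WP 3 and Cluster randomized controlled trial state that GPs are randomised as groups, two groups in each of three boroughs.

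**The concern.** A target difference is normally justified either as the effect expected or as the smallest that matters. The power section does neither, and the background supplies no figure. On the wider literature it says "Research-based knowledge about the effect of shared care is inconclusive". On the forms of collaboration tried in Norway it says "we have little knowledge on how they function and whether they contribute to better patient satisfaction and better outcome". The Canadian experience is favourable ("It has also demonstrated significant improvement in up to 70% of patients") but comes with no satisfaction difference.

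Dilution adds to the doubt. The outline of the model says "There may be one team serving all the three GP groups", and those groups would serve about 20 100 / 2 = 10 050 patients a year. If only some attenders meet the team, a mean shift of 0.5 SD over everyone requires a larger gain in those who do: 0.5 / 0.5 = 1.0 SD if half gain, 0.5 / 0.25 = 2.0 SD if a quarter gain. If the true mean effect were smaller, 9 per GP would be too few, and a null result would have no stated limit to be read against.

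**Working it through.** **1. The protocol's own figures.** Alpha is not stated; two-sided 5 % is assumed.
- Individual randomisation: n = 2 × [(1.960 + 1.282) / 0.5]² = 84.06, so 85 per arm.
- Clustered: 85 × [1 + (85/12 − 1) × 0.03] = 100.5, so 101 per arm. 101 / 12 = 8.4, so 9 per GP (108 per arm).
- Solving with the final cluster size instead gives 85 × 0.97 / (1 − 85 × 0.03/12) = 104.7, so 105, which 9 per GP still covers.

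Both stated figures reproduce. They depend only on the ratio 0.5, so it does not matter here whether 3.8 is read as half the SD (SD 7.6) or as the SD itself.

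**2. Is 9 per GP what the trial will recruit?** 1350 / 2 = 675 per arm with an equal split, and 675 / 12 = 56.25 per GP, about 6.7 times the requirement. Every patient seen in the four weeks is to be approached, and no rule stops recruitment at nine. A larger required number, such as 19 per GP for 0.4 SD or 29 for 0.35 SD, would change nothing in the conduct.

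Those two numbers also come from a different method (noncentral t, 22 df) from the one behind the protocol's 9. By the protocol's one-step method:
- 0.4 SD: 132 × [1 + (11 − 1) × 0.03] = 171.6, so 172 per arm, or 15 per GP.
- 0.35 SD: 172 × [1 + (172/12 − 1) × 0.03] = 240.8, so 241 per arm, or 21 per GP.

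**3. The detectable difference at 675 per arm.** SE in SD units = √[2 × (ICC + (1 − ICC)/m) / k], with k clusters per arm and m patients per cluster.

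| Cluster | k | m | SE | Detectable at 90 %, normal | Detectable at 90 %, noncentral t | Power for 0.30 SD (t) |
|---|---|---|---|---|---|---|
| GP | 12 | 56.25 | 0.0887 | 0.29 SD | 0.30 SD (22 df) | 90 % |
| GP group, as randomised | 3 | 225 | 0.1512 | 0.49 SD | 0.66 SD (4 df) | 33 % |

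The second row assumes one group per borough in each arm, equal group sizes, and that the ICC of 0.03 also holds between groups; the protocol gives no group-level ICC. At a group-level ICC of 0.01 the limit is about 0.43 SD (t, 4 df), still above 0.30. At 0.03, even unlimited patients per group leave it at about 0.62 SD. Both rows compare the arms after implementation only, whereas the protocol plans a difference-in-difference model with WP1 as baseline.

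**4. The dilution argument.** The shares of 50 % and 25 % are assumptions; the protocol states none. The sentence on one team goes on to allow separate teams or sub-teams, within an outline labelled as suggested, and the model was to be specified later. The source model treats physical as well as mental illness, so benefit need not be confined to a small subgroup. The protocol also says that research on collaboration has mainly studied simpler models, so inconclusive results there do not contradict 0.5 SD here.

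**The case for a change.** The best case for the concern is that target and requirement are fixed in this document, not deferred, and that no reason is given. A trial that only just met 9 per GP would have weak power for smaller effects. On the GP basis (noncentral t, 22 df, 108 per arm), power is 88 % at 0.5 SD, 71 % at 0.4 SD and 47 % at 0.3 SD. The same four weeks are expected to yield far more patients, so stating what they can detect would cost one sentence.

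The factual part of this stands: no rationale is given, and the GP-level figures are correct. A sentence of rationale would help a reader. But a missing rationale is not a misstatement, and reasonable statisticians differ on which difference to target. The low power at nine per GP describes a trial that the recruitment plan does not lead to. The detection-limit sentence would do harm: 0.30 SD (2.3 points if the SD is 7.6) would make a null result look much more informative than three randomised groups per arm may allow. A null result is in any case better read against the confidence interval from an analysis that respects the randomised units.

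**Conclusion.** The concern does not hold. The figures of 85 and 101 per arm are right for the inputs stated, no passage contradicts the half-SD target, and the expected recruitment of about 56 per GP is well above the minimum of 9. What remains is a wish for explanation, and the dilution argument behind it depends on shares that the protocol does not give. The GP-level limit of 0.30 SD should not be written into the plan: at group level, with ICC 0.03 carried over, the figure is about 0.66 SD.

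This conclusion assumes two-sided 5 %, an equal split of the 1350 and no loss to the mailed questionnaires. It covers only the choice and reporting of the target difference. Whether the power calculation should count GP groups instead of GPs is a separate question and is not settled here.
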